9.2.4 Treatment as Usual (TAU)

Participants assigned to the TAU group will receive the standard treatment for opioid use disorder provided at each HIV clinic. The standard of care in U.S. HIV clinics is currently to link with opioid agonist treatment services. Opioid substitution therapy is recommended for HIV-infected participants with opioid dependence [35, 104], and many HIV practices are being encouraged to adopt clinic-based BUP/NX [105]. Assessment of TAU includes assessing use of medication-assisted treatments for alcohol use disorder as well as opioid use disorder since we anticipate some participants with OUD will also have AUD. TAU assessment will also include characterization of usual counseling services and linkages with local detox programs available at each site.

Many HIV clinics receive funding from the Ryan White Care Act for case management and addiction/mental health counseling services to facilitate engagement of HIV-infected patients with substance use disorders in treatment. In a 6-month randomized trial of methadone maintenance referral strategies, passive referral of heroin users resulted in 8% methadone maintenance enrollment at 6 months vs. 29% enrollment among those randomized to case-management assisted referrals ($p = .006$) [139].

During the formal site selection process, a thorough assessment will be conducted of each site’s standard practice for linkage to addiction treatment services. Throughout the course of the trial, HIV clinics will be monitored for any potential changes that might occur in standard practice around linking HIV-infected clinic patients to substance use treatment.

9.3 Ancillary Treatments

Participants who experience withdrawal symptoms or nausea associated with detoxification and induction may be treated with ancillary medications (see guidelines in study Manual of Operating Procedures (MOP)). Depression is also common in opioid-dependent participants and, though not causally related to XR-NTX use, may adversely affect prognosis of naltrexone treatment [140,

141]. Participants who show depressive symptoms may be treated by their HIV clinic providers with antidepressants and/or referred for mental health evaluation and treatment.

9.4 Provisions for Access to Treatment after Study

Prior to the conclusion of the 24 week active treatment phase, the research team will make an effort to arrange for continued treatment with XR-NTX as locally available and appropriate. In most cases, the study physician will continue to prescribe this FDA-approved study medication as the participant's HIV primary care provider. Where this is not possible (due to insurance or availability of treatment resources, etc.), alternative treatment referrals (e.g., methadone maintenance, intensive outpatient psychosocial aftercare), special access programs, and manufacturer medication assistance plans will be made as appropriate.

9.5 Drug Packaging / XR-NTX

XR-NTX will be supplied in single use kits. Each kit will contain one 380 mg vial of Vivitrol® microspheres, one vial containing 4 mL (to deliver 3.4 mL) diluent for the suspension of Vivitrol®, one 5-mL prepackaged syringe, one 1-inch 20-gauge needle, two 1.5-inch 20-gauge needles and two 2-inch 20-gauge needles with needle protection devices. The lot number will be included on the kit labels as supplied by the manufacturer.

9.6 Participant Discontinuation

All participants will be followed for the duration of the study (25-28 weeks, depending on length of time required for completion of screening and enrollment procedures) unless they withdraw consent, or the investigator or sponsor decides to discontinue their enrollment. Reasons for the investigator or sponsor terminating a participant from the study may include, but are not limited to, the participant becoming a threat to self or others, lack of funding, or DSMB early termination of the study for safety or effectiveness reasons.

9.7 Blinding

CTN-0067 is an unblinded study.

9.8 Participant Compensation

Participants will be compensated for their time and effort for baseline and follow-up visits. Participants may receive a maximum amount of up to approximately \$510.00 U.S. Dollars for completing the following activities: screening interview, baseline assessment, and visits at 1, 4, 8, 12, 16, 20, and 24 weeks. The specific amounts and format (e.g., cash, debit card, voucher, etc.), and distribution schedule will be determined by the participating site with the approval of the Lead Investigator or Co-Lead Investigators and the IRB. All compensation will be recorded and tracked in the Compensation Log.

9.9 Long Term Mortality Follow-up

In the future, we will attempt to account for all participants who may have died after the study ends. We will do this by sending participant data to the National Center for Health Statistics' (part of the Centers for Disease Control and Prevention) National Death Index. This is a list of all persons who have died in the U.S. Data, if available, will be abstracted from the Locator Form and other CRFs and may include name, date of birth, sex, race/ethnicity, social security number, state of residence, date of last contact, and date of death. The date and cause of death identified

by the National Death Index will be entered into a secure database at OHSU. Information regarding persons presumed to still be alive in the National Death Index will be destroyed.

10.0 STUDY ASSESSMENTS AND INSTRUMENTS

The selected assessments attempt to balance the value of comprehensive data against the costs of data collection in terms of staff time, feasibility of completing assessments in an outpatient HIV clinic setting, financial cost, and response burden. Therefore, assessments have been limited to those that contribute directly to the study objectives or that are necessary for reasons of safety or regulatory compliance. When choosing between comparable instruments, we have chosen instruments for which CRFs have already been built for other recent CTN trials to minimize the cost of new CRF construction.

10.1 List of all CRFs and Table of Assessments

Assessment/Activity	Pre-Screening	Screening	Baseline	Randomization ^{^^}	Treatment Initiation	Safety Visit	Week 4	Week 8	Week 12	Week 16	Week 20	Week 24	End of Study (#Week 24)	As Needed
Enrollment														
Pre-Screening Verbal Consent and HIPAA Authorization/Waiver	X													
Pre-Screening Interview	X													
Demographics (from PhenX)		X												
Master Enrollment Log ⁺⁺		X	X											
Informed Consent/HIPAA		X												
Inclusion/Exclusion Checklist				X										
Locator Form ⁺⁺		X	X	X	X	X	X	X	X	X	X	X		
Medical Release ⁺⁺		X												X
Study Administration														
Inventory Form														X
Pre-screening Log ⁺⁺	X													
Secure Document Upload		X												X
Missed Visit Form														X
Progress Note Checklist ⁺⁺		X	X	X	X	X	X	X	X	X	X	X		
Protocol Deviation														X
Visit Compensation Log ⁺⁺		X	X	X	X	X	X	X	X	X	X	X		
End of Treatment													X	X
Study Completion													X	X
Safety and Medical Measures														
Adverse Events			X	X	X	X	X	X	X	X	X	X		X
ARV Medication Log			X										X	X
Concomitant Medications		X												
CBC		X											X	X
CD4 Count				X					X				X	X
Serum Creatinine		X											X	X
Confirmed Pregnancy and Outcome														X
Detoxification					X									
Fatal Opioid Overdose														X

Assessment/Activity	Pre-Screening	Screening	Baseline	Randomization ^{^A}	Treatment Initiation	Safety Visit	Week 4	Week 8	Week 12	Week 16	Week 20	Week 24	End of Study (#Week 24)	As Needed
Vital Signs (blood pressure, pulse, temperature, height and weight)		X											X [±]	X [±]
Hepatitis B surface antigen (HBs AG)				X										
Hepatitis C virus antibody (HCV ab)				X									X ^{**}	
Hepatitis C PCR confirmation, when HCV ab +				X ^{**}									X ^{**}	
HIV-1 RNA PCR		X								X			X	X
LFT (AST, ALT) and INR		X								X			X	X
Medical and Psychiatric History		X												
Medication Adherence			X		X		X	X	X	X	X	X	X	
Pain Assessment			X				X	X	X	X	X	X	X	X
Non-Fatal Opioid Overdose			X										X	X
PBMC				X						X			X	X
Physical Examination		X												
Pregnancy and Birth Control Assessment (including urine pregnancy test)			X		X ^{*,^}	X ^{*,^}	X	X	X	X	X	X	X	
Naloxone Challenge*														X
XR-NTX Administration Log* ⁺⁺					X		X	X	X	X	X			
XR-NTX Injection*					X		X	X	X	X	X			
Injection Site Abnormality*														X
Injection Site Examination*						X	X	X	X	X	X	X	X	
ASI Lite Drug/Alcohol Use			X										X	X
Concise Health Risk Tracking – Self Report			X		X	X	X	X	X	X	X	X		
Concise Health Risk Tracking – Clinician Rated														X
DSM-5 Substance Use Disorders		X												
Urine Drug Screen		X			X*	X*	X	X	X	X	X	X	X	
HIV Care Utilization			X										X	X
Buprenorphine and Methadone Chart Abstraction							X	X	X	X	X	X	X	
Quality of Life, from PhenX			X											
Quality of Life, from EQ-5D			X									X	X	

Assessment/Activity	Pre-Screening	Screening	Baseline	Randomization ^{^A}	Treatment Initiation	Safety Visit	Week 4	Week 8	Week 12	Week 16	Week 20	Week 24	End of Study (#Week 24)	As Needed
Risk Assessment Battery			X				X	X	X	X	X	X	X	
Tobacco Use History and Substance Use History, from PhenX			X									X	X	
Timeline Follow Back			X		X		X	X	X	X	X	X	X	
Treatment Plan				X			X	X	X	X	X	X	X	
Treatment Initiation***													X	X
XR-NTX Non-Initiation*														X
Treatment Satisfaction Survey													X	X
Treatment Services Review			X		X		X	X	X	X	X	X	X	
VACS Index				X									X	X
Visual Analog Scale			X				X	X	X	X	X	X	X	
PHQ-9 Depression Symptoms			X						X			X	X	
Suicidal Risk														X
Criminal Justice			X						X			X	X	
Participant Treatment Preference			X											

* Only for participants randomized to the XR-NTX arm.

**At randomization, HCV PCR confirmation is required when HCV ab is positive. At 24 weeks, collect HCV ab if participant tested HCV ab negative at randomization or if HCV ab result was not obtained at randomization. At 24 weeks, collect HCV PCR confirmation if: HCV antibody is positive at randomization, but HCV PCR was not obtained at randomization or HCV antibody was negative at randomization, but HCV antibody is positive at Week 24.

*** Only for participants randomized to TAU arm.

[‡] Height and weight only for BMI calculations.

⁺⁺ Not captured in eClinical.

[^]Urine pregnancy test required for XR-NTX group only; remainder of Pregnancy and Birth Control Assessment required for all participants.

^{^A}Assessments performed at randomization correspond with Week 0 requirements in the eClinical system.

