- 2) **Patient Acceptability.** Patients were interested in XR-NTX treatment, as well. The study site in Vancouver, B.C. conducted a survey of 657 persons who inject opioids as part of their site selection application. About half (52%) of the survey participants expressed willingness to receive XR-NTX treatment for opioid use disorder. Daily heroin injection was associated with increased willingness to try XR-NTX (OR 1.53, 95% CI 1.02, 3.12) [107]. Prospective CTN-0055 CHOICES pilot study participants (n=112) were asked about their willingness to participate in a trial of XR-NTX during pre-screening. Ninety-eight percent of prospective participants interested in reducing opioid use (n=60) and 99% of those interested in reducing alcohol use (n=82) were definitely or maybe willing to consider enrolling in a clinical trial of XR-NTX.
- 3) **Randomization Rate.** The CTN-0055 CHOICES pilot study enrolled 51 HIV-infected patients receiving care at two pilot site HIV clinics (mean age 46 years, mean CD4 count 620; 43% women). The trial achieved 155% actual versus expected randomizations, reaching randomization targets 4 months ahead of schedule and enrolling 22 (43%) participants with opioid and 29 (57%) with alcohol as their primary use disorder. Sixteen percent of randomized participants met criteria for *both* opioid and alcohol use disorders. Overall, the pilot study enrolled a mean of 3 participants per month per site.
- 4) **Treatment Initiation.** The majority (68%) of participants assigned to XR-NTX initiated treatment. Five of 12 (42%) participants with any OUD assigned to XR-NTX initiated XR-NTX within 4 weeks of randomization. The CTN-0055 CHOICES pilot study randomized participants prior to detoxification and provides the first benchmark for XR-NTX treatment initiation in community-dwelling people with opioid use disorder. Both of the two clinical trials of XR-NTX for opioid use disorder that led to FDA approval required successful residential detoxification prior to randomization and did not report treatment initiation rates [54, 55]. The CTN-0067 scale-up trial seeks to increase the rate of treatment initiation for participants with OUD with a modified naltrexone induction protocol (Section 9.2.3.1).

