9.2.3 Clinic-based Extended-Release Naltrexone (XR-NTX)

9.2.3.1 *XR-NTX Detoxification and Induction (0 - 4 weeks duration, during active treatment phase)*

Following randomization, participants assigned to office-based XR-NTX will undergo detoxification and naltrexone induction in accordance with the package insert and published guidelines [133-136]. Participating HIV providers will be trained to manage outpatient detoxification procedures for participants with mild to moderate anticipated opioid withdrawal severity. Provider training reviews a range of detox options outlined in the Manual of Operating Procedures [137, 138]. Participants failing an induction regimen and those with anticipated severe withdrawal may be referred to local detox facilities for medication-assisted inpatient detoxification.

9.2.3.2 *Active Treatment with XR-NTX (Treatment Initiation through Week 20)*

XR-NTX (4cc, ~380mg of naltrexone base) will be administered *approximately* every four weeks (treatment initiation visit and weeks 4, 8, 12, 16, and 20) for an approximate maximum of 6 doses in the form of Vivitrol®, which will be obtained by NIDA or the NIDA contractor for distribution to the sites. Administration of XR-NTX more frequently will require approval by the Lead Investigators and will be provided on a case-by-case basis. XR-NTX will be administered by intramuscular injection to the buttocks (alternating sides monthly) according to the injection preparation and administration procedures specified in the Vivitrol® product package insert. These procedures are designed to minimize the risk of injection site reactions.

9.2.3.3 *Handling of Missed XR-NTX Doses, Lapses, and Relapses*

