19.3.2 Serious Adverse Events

For the purpose of this study, the following events will not be reported as an SAE, but will be recorded on study specific forms in the data system.

- 1) Detox admissions (documented instead on the DTX form).**
- 2) Admission for labor and delivery (documented instead on the Confirmed Pregnancy and Outcomes form).**
- 3) Admission for elective or pre-planned surgery.**

The Lead Node will report all other SAEs on the Serious Adverse Event form in the data system. Sites must determine if local IRBs will require annual or other SAE reporting.

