19.4 Known Potential Toxicities of Study Drug/Intervention

Refer to the package insert for XR-NTX.

19.5 Known Potential Adverse Events Related to the Underlying Clinical Condition and/or Study Populations

Each of the participating research sites has established practices for managing medical and psychiatric emergencies, and the study staff will continue to utilize these procedures. Treatment providers at each research site will be responsible for monitoring participants for possible clinical deterioration or other problems, and for implementing appropriate courses of action.

As this population will have significant ongoing health and substance use issues, events related to complications of HIV, substance use treatment or admission for substance detoxification will be captured on study-specific forms and not duplicitely reported as an adverse or serious adverse event. All hospitalizations for other (non-HIV, non-substance-use related) medical, surgical and psychological reasons and deaths will be reported on AE/SAE forms. These data will still be included in the reports to the DSMB at the regular meetings.

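### Detox admissions are excluded from AE/SAE reporting in favor of a form that the schedule lists only at Treatment Initiation

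*Combined protocol and SAP*

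**What the plan says.** Section 19.3.2 states that "the following events will not be reported as an SAE, but will be recorded on study specific forms in the data system". The first item on its list is "Detox admissions (documented instead on the DTX form").

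Section 19.5 covers AEs as well as SAEs: "admission for substance detoxification will be captured on study-specific forms and not duplicitely reported as an adverse or serious adverse event". It closes with "These data will still be included in the reports to the DSMB at the regular meetings". I read that sentence as including the detox admissions, since the word still has little purpose otherwise.

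In Section 10.1 the "Detoxification" row has a single mark, under Treatment Initiation. It has none at Weeks 4 to 24, End of Study or As Needed.

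Section 9.2.3.1 foresees admissions away from that visit: "Participants failing an induction regimen and those with anticipated severe withdrawal may be referred to local detox facilities for medication-assisted inpatient detoxification". Section 9.2.3.3 foresees missed injections and a return to opioid use after treatment has started.

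**The concern.** Taking an expected event out of SAE reporting is reasonable when another form captures it reliably. Here the safety text makes that exchange, but the schedule lists the replacement form at one visit only. For the XR-NTX arm, Sections 9.2.3.2 and 9.2.3.4 make Treatment Initiation the visit of the first injection. A participant admitted for detoxification who never reaches an injection has no visit at which the form falls due. Anyone admitted after starting treatment is already past that visit.

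Inpatient hospitalization is one of the seriousness criteria in Section 23.1, so at least some of these admissions would be SAEs without the exclusion. The arms also differ in their need for detoxification. It precedes the injection in the XR-NTX arm (Section 9.2.3.1), whereas usual care is mainly linkage to agonist treatment (Section 9.2.4). Patchy capture in an open-label trial could therefore distort a comparison of the arms, and the DSMB would have no specified table in which to see it.

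**Working it through.** The plan gives no figure for this point and no arithmetic applies. The check is a comparison of sections.

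**1. Is the row the DTX form?** This is inferred from the name. No other row title in Section 10.1 refers to detoxification.

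**2. What does the row show?** The table has 14 visit columns. The only mark is in the fifth, Treatment Initiation, and columns 6 to 14 are empty. The row directly above (Confirmed Pregnancy and Outcome) and the row directly below (Fatal Opioid Overdose) each have one mark, under As Needed. So does XR-NTX Non-Initiation. The table thus has a convention for event-driven forms, and this row does not follow it. The row has no asterisk restricting it to XR-NTX, so it applies to both arms.

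**3. Could a misread table explain it?** Some cells are displaced in the text I worked from. HIV-1 RNA PCR reads as Week 16, where Section 13.5 says week 12. CD4 count, in the same block as Detoxification, reads as Randomization and Week 12, which agrees with Section 13.5. If the Detoxification mark were one column out, it would belong to Randomization or to the Safety Visit. Either way there is one early mark and no As Needed mark.

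**4. When is the form due?**

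| Detox admission | Sections 19.3.2 and 19.5 | Section 10.1 |
|---|---|---|
| Before initiation, treatment started later (XR-NTX allowed until week 20, Section 9.1.9) | Record it | Due at the initiation visit, possibly late |
| Participant never initiates | Record it | Never due |
| After initiation, either arm | Record it | Not due again |

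The sections agree in the first case and conflict in the other two.

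**5. What else would catch these admissions?**
- Treatment Services Review (Section 14.5): asks both arms about detoxification and inpatient services at baseline, treatment initiation and every 4 weeks to week 24. It is self-reported, covers the past 28 days, and is meant to measure usual-care and counseling exposure.
- Record abstraction (Section 9.1.6): covers addiction-service use up to 52 weeks after randomization, for the stated purpose of evaluating secondary outcomes.
- XR-NTX Non-Initiation form (Section 12.10): tracks the absence of any injection. Admissions are not mentioned.
- Paper AE log (Section 19.3.1): takes all AEs, but Section 19.5 says detox admissions are not reported as AEs. Whether they appear there is unclear.

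These sources give partial capture. None is described as an event-level safety record of detox admissions.

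**6. Where would they be reported?** Section 17.13 specifies summaries of AEs and SAEs only. Even a completed Detoxification form feeds no specified by-arm safety table.

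**The case against.** The best defense is that the duty to record is not tied to a visit. Sections 19.3.2 and 19.5 require these admissions to be entered and shown to the DSMB whenever they happen. The schedule is visibly incomplete elsewhere: Concomitant Medications is marked only at Screening although Section 24.2.5.3 has it assessed at each clinic visit, and the self-report CHRT has no End of Study mark although Section 15.5 provides for one. A blank cell therefore does not prove that nothing is collected. Completion rules may also sit in the CRF and operations manuals named in Section 20.4, which are not part of these documents.

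All of this stands. It makes the defect a conflict between schedule and text, not a rule that drops events. It does not remove the conflict, because sites work from the schedule.

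A reader might go further and infer that the plan loses these hospitalizations and that DSMB reports will understate the burden of XR-NTX. The documents do not support that. Recording is still required and the Treatment Services Review covers both arms. Section 9.2.3.1 speaks of local detox facilities, and not every such admission is shown to be a hospitalization under Section 23.1. Section 17.13 plans no by-arm hospitalization result that could be biased.

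It is also tempting to put a number on the gap from the pilot (Section 4.3): "Five of 12 (42%) participants with any OUD assigned to XR-NTX initiated XR-NTX within 4 weeks of randomization". The other 7 of 12, applied to 175 per arm, give 175 × 7/12 ≈ 102 participants. That figure counts people who had not started by week 4, not admissions or missing forms. No document says the pilot's seven were admitted. Initiation is allowed until week 20, outpatient detoxification is planned for milder cases, and the induction protocol has been changed to raise initiation. The figure should not be used.

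**Conclusion.** The point holds as a contradiction between Section 10.1 and Sections 19.3.2 and 19.5. It concerns admissions after initiation and participants who never initiate. For these, the schedule as written makes no event-level form due, and Section 17.13 names no by-arm summary in which the admissions would appear. Capture may be incomplete and may differ by arm. Neither can be sized, because the documents give no detox-admission rate.

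The conclusion assumes that the DTX form is the Detoxification row and that the row has no As Needed mark in the source PDF, which the reader can confirm directly. The correction is worth making because it is cheap and delivers what the safety text already promises.

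**What to change.** - **Section 10.1:** reconcile with Sections 19.3.2 and 19.5 by marking the Detoxification form As Needed in both arms from randomization to end of study. State that it is completed for each detox admission, whether or not a Treatment Initiation visit takes place. Use one name for the form throughout.
- **Section 17.13:** add a by-arm count of detox admissions (participants with at least one, and total events) among all randomized participants, for the DSMB reports and the final report.

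The cost is one mark in the schedule, a completion note, a little extra form entry at sites and one more table. Nothing in participants' care changes.
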